8.1.5.1 Vineland Adaptive Behavior Scale, Third Edition (Vineland™-3)

The Vineland[™] is an instrument that measures communication, daily living skills, socialization, motor skills (only used in children up to 9 years of age) and maladaptive (not assessed in this study) behaviors of individuals with developmental disabilities (Sparrow et al 2005). The Comprehensive Interview will be administered to a participant's support person in this study, during which the rater or clinician will ask to the support person open-ended questions relating to the participant's activities and behavior. Domain scores will be obtained for the individual domains of Socialization, Communication, and Daily Living Skills and used to calculate the Vineland[™] Adaptive Behavior Composite score. Standardized scores on the Adaptive Behavior Composite score range from 20 to 160, with higher scores indicating better adaptive functioning.

VinelandTM-3 will be administered at different visits (see SoA in Section 1.3) by central raters via live, secure telemedicine platform. For any individual participant, the same rater should administer the VinelandTM.

This interview will take approximately 45 to 60 minutes. The rater will interview the support person to complete the VinelandTM.

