4.1.2 Baseline Definitions

Unless otherwise stated, baseline is defined as the last observation recorded before the first study drug administration. The last observation can be an unscheduled / repeated measurement. If a pre-treatment observation is missing, then the pre-baseline (preferred) or screening value may be used.

As the age at screening was determining the choice of questionnaires, and for reasons of consistency, the age at screening was chosen to be the analysis age.

ECG baseline is defined as the mean of the triplicate measurement before the first study drug administration on Day 1.

4.1.3 Characteristics of Efficacy Endpoints

Vineland-3

The Vineland-3 (Sparrow et al. 2016) is a semi-structured interview that measures an individual's adaptive behaviour across three domains of communication, socialisation and daily living skills. Additional domains of motor skills (only used in children up to 9 years of age) and maladaptive behaviours were not captured in this study. Each adaptive behaviour domain is composed of three subdomains. Subdomain raw scores are used to derive two types of scores: Standard (V-scale scores; range from 1-24) and Growth Scale Values (GSVs). Standard scores are scores relative to a normative age group and can range from 20-140. A GSV is a person-ability score that is used to track an individual's progress. A higher score indicates better adaptive functioning.

Repetitive Behaviour Scale-Revised (RBS-R)

The RBS-R (Bodfish, 1999) is a 43-item informant-based questionnaire, assessing the variety of restricted and repetitive behaviours observed in individuals with ASD. A total RBS-R score is calculated as the sum of the scores for the 43 items. The total RBS-R score ranges from 0 to 129, with a higher score indicating more severe repetitive and restrictive behaviours. The RBS-R subscale scores will also be calculated as the sum of the scores for each item within each subscale.

Caregiver-Reported Routines Inventory (CRRI)

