Clinical Global Impressions Scale - Severity (CGI-S) Domain score	An impairment rating score with 7 categories (no symptoms to very severe symptoms) for each of the following domains: - communication/speech - activities of daily living - social functioning - disruptive behavior - restricted and repetitive behavior Note: The customizable "other" symptom domain will not be summarized.
Clinical Global Impressions Scale - Severity (CGI-S) Overall score	A rating score with 7 categories (no symptoms to very severe symptoms) for the overall rating.

Clinical Global Impressions Scale - Improvement (CGI-I) Domain score	A rating score with 7 categories (very much improved to very much worse) for each of the following domains: - communication/speech - activities of daily living - social functioning - disruptive behavior - restricted and repetitive behavior Note: The customizable "other" symptom domain will not be summarized.
Clinical Global Impressions Scale - Improvement (CGI-I) Overall score	A rating score with 7 categories (very much improved to very much worse) for the overall rating.
Vineland-3 ABC standard score	A raw score will be calculated for each subdomain of the Socialization (interpersonal relationships, play and leisure time, coping skills), Communication (receptive, expressive, written) and Daily Living Skills (personal, domestic, community) domain as the sum of the scores for each item within the subdomain. The raw scores for each of the 9 subdomains will be mapped to V-scale scores relative to a normative age group as described in the Vineland-3 scoring manual (Sparrow et al. 2016). A standard score will be calculated for each of the three domains (Communication, Socialization and Daily Living Skills) as the sum of the V-scale scores within each domain. The Vineland-3 ABC standard score will be calculated as the sum of the standard scores for the three domains.
Vineland-3 Socialization standard score	A raw score will be calculated for each subdomain of the Socialization domain (interpersonal relationships, play and leisure time, coping skills) as the sum of the scores for each item within the subdomain.
	The raw scores for each of the 3 subdomains will be mapped to standard (V-scale) scores relative

	to a normative age group as described in the Vineland-3 scoring manual (Sparrow et al. 2016) The Vineland-3 Socialization standard score will be calculated as the sum of the V-scale scores within each subdomain.

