Vineland-3 Communication standard score	A raw score will be calculated for each subdomain of the Communication domain (receptive, expressive, written) as the sum of the scores for each item within the subdomain. The raw scores for each of the 3 subdomains will be mapped to standard (V-scale) scores relative to a normative age group as described in the Vineland-3 scoring manual (Sparrow et al. 2016) The Vineland-3 Communication standard score will be calculated as the sum of the V-scale scores within each subdomain.
Vineland-3 Daily Living Skills standard score	A raw score will be calculated for each subdomain of the Daily Living Skills domain (personal, domestic, community) as the sum of the scores for each item within the subdomain. The raw scores for each of the 3 subdomains will be mapped to standard (V-scale) scores relative to a normative age group as described in the Vineland-3 scoring manual (Sparrow et al. 2016). The Vineland-3 Daily Living Skills standard score will be calculated as the sum of the V-scale scores within each subdomain.
Beck Anxiety Inventory (BAI)	The BAI total score will be calculated as the sum of the scores for each of the 21 items.
Parent Rated Anxiety Scale- ASD (PRAS-ASD)	The PRAS-ASD total score will be calculated as the sum of the scores for each of the 25 items.
Adolescent/Adult Sensory Profile (AASP)	Quadrant raw scores will be calculated as the sum of the scores for items within each of the following quadrants:

	 low registration (items 3, 6, 12, 15, 21, 23, 36, 37, 39, 41, 44, 45, 52, 55 and 59) seeking (items 2, 4, 8, 10, 14, 17, 19, 28, 30, 32, 40, 47, 50 and 58) sensitivity (items 7, 9, 13, 16, 20, 22, 25, 27, 31, 33, 34, 48, 51, 54 and 60) avoiding (items 1, 5, 11, 18, 24, 26, 29, 35, 38, 43, 45, 49, 53, 56 and 57) Reference: Adolescent/Adult Sensory Profile
Short Sensory Profile (SSP-2)	The SSP-2 sensory raw score will be calculated as the sum of the scores for items 1-14. The SSP-2 behavioral raw score will be calculated as the sum of the scores for items 15-34. Quadrant raw scores will be calculated as the sum of the scores for items within each of the following quadrants: - seeking (items 6-8, 11, 14, 31 and 32) - avoiding (items 16-20 and 22-26) - sensitivity (items 1-5, 21, 25, 28, 29 and 33) - registration (items 9, 10, 12, 13, 15, 27, 30 and 34) Reference: Short-Sensory Profile-2 Caregiver Questionnaire

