4.2 PRIMARY, SECONDARY AND EXPLORATORY EFFICACY ANALYSIS

The primary efficacy analysis evaluates the mean change from baseline to 12 weeks of treatment as measured by the Vineland-3 ABC three-domain GSV composite. The difference in the mean change from baseline between each of the two active doses and placebo will be extracted as contrasts from the ANCOVA model.

The efficacy analyses of the secondary endpoints and of the CRRI total score evaluate the mean change from baseline to 12 weeks of treatment. The difference in the mean change from baseline of the two active doses and placebo will be extracted as contrasts from the ANCOVA model.

The efficacy analysis of CGI-I evaluates the overall score at 12 weeks of treatment. The difference of the two active doses and placebo will be extracted as contrasts from the ANCOVA model.

4.2.1 Definition of Primary Endpoint

The primary endpoint is Change from baseline to Week 12 in the Adaptive Behavior Composite score of the Vineland[™] Adaptive Behavior Scales, Third Edition (Vineland[™]-3), as defined in Section 1.1 of SAP (see Table 1).

4.2.2 Main Analytical Approach for Primary, Secondary, CRRI and CGI-I Endpoints

The analyses of primary, secondary, CRRI and CGI-I efficacy endpoints will include all participants in the Efficacy Analysis Population.

An analysis of covariance (ANCOVA) model will be used to compare treatment effects for the primary, secondary, CRRI and CGI-I efficacy endpoints across the overall Efficacy Analysis Population of adolescents and adults. The model will include treatment as main effect, individual age at screening, IQ, and baseline score as covariates. Treatment differences will be estimated together with their 80% confidence intervals as derived from the model and their associated p-values.

The ANCOVA model will be applied to change from baseline data y_{ij} of participants i, and treatment $j \in \{\text{placebo (reference)}, \text{low dose}, \text{high dose}\}\)$ as follows:

$$y_{ij}=\mu+t_i+a_i+IQ_i+BL_i+\epsilon_{ij}$$

where μ gives the overall endpoint mean change, followed by the fixed effect t which models the effect of treatment, age a, IQ, the endpoint baseline value BL, and ϵ , which gives the overall error term with $N(0, \sigma_{\epsilon}^2)$.

Table 8 Efficacy Statistical Analysis Methods

Endpoint	Statistical Analysis Methods
Primary	ANCOVA
Secondary	
CRRI, CGI-I	

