t_vabs3_ancov a	Efficacy	Vineland-3 SOC GSV Score ANCOVA age interaction
t_vabs3_ancov a	Efficacy	Vineland-3 SOC GSV Score ANCOVA IQ interaction
t_vabs3_ancov a	Efficacy	Vineland-3 COM GSV Score ANCOVA no interactions
t_vabs3_ancov a	Efficacy	Vineland-3 COM GSV Score ANCOVA age interaction
t_vabs3_ancov a	Efficacy	Vineland-3 COM GSV Score ANCOVA IQ interaction
t_vabs_cfb	Efficacy	Vineland-3 ABC GSV Score Change from Baseline
t_vabs_cfb	Efficacy	Vineland-3 SOC GSV Score Change from Baseline
t_vabs_cfb	Efficacy	Vineland-3 COM GSV Score Change from Baseline
t_vabs_cfb	Efficacy	Vineland-3 DLS GSV Score Change from Baseline
t_vabs_cfb	Efficacy	Vineland-3 ABC Standard Score Change from Baseline
t_vabs_cfb	Efficacy	Vineland-3 SOC Standard Score Change from Baseline
t_vabs_cfb	Efficacy	Vineland-3 COM Standard Score Change from Baseline
t_vabs_cfb	Efficacy	Vineland-3 DLS Standard Score Change from Baseline
t_rbsr_ancova	Efficacy	RBS-R Total Score ANCOVA no interactions
t_rbsr_ancova	Efficacy	RBS-R Total Score ANCOVA age interaction
t_rbsr_ancova	Efficacy	RBS-R Total Score ANCOVA IQ interaction
t_rbsr_cfb	Efficacy	RBS-R Total Score Change from Baseline
t_rbsr_cfb	Efficacy	RBS-R Subscale Score (3FM) Change from Baseline

[figure not shown]
t_crri_ancova	Efficacy	CRRI Total Score ANCOVA no interactions	
t_crri_ancova	Efficacy	CRRI Total Score ANCOVA age interaction	
t_crri_ancova	Efficacy	CRRI Total Score ANCOVA IQ interaction	
t_crri_cfb	Efficacy	CRRI Total Score Change from Baseline	
t_crri_cfb	Efficacy	CRRI Subscale Score (5FM) Change from Baseline	
t_cgii_ancova	Efficacy	CGI-I Overall Score ANCOVA no interactions	
t_cgii_ancova	Efficacy	CGI-I Overall Score ANCOVA age interaction	
t_cgii_ancova	Efficacy	CGI-I Overall Score ANCOVA IQ interaction	
t_cgii_mmrm	Efficacy	CGI-I Overall Score MMRM	
t_cgii	Efficacy	CGI-I Overall Score	
t_cgii_cat	Efficacy	CGI-I Proportions per Rating Category	
t_cgis	Efficacy	CGI-S Overall Score	
t_cgis_cat	Efficacy	CGI-S Proportions per Rating Category	
t_bai_cfb	Efficacy	BAI Total Score Change from Baseline	
t_pras_cfb	Efficacy	PRAS-ASD Total Score Change from Baseline	
t_ssp_cfb	Efficacy	SSP-2 Summary Score Change from Baseline	
t_aasp_cfb	Efficacy	AASP Quadrant Summary Score Change from Baseline	
t_promis_cfb	Efficacy	PROMIS Sleep-Disturbance T-Score Change from Baseline	
t_promis_cfb	Efficacy	PROMIS Sleep Related Impairment T-Score Change from Baseline	
t_<>	Efficacy	Change from Baseline in EEG beta power	

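### SAP Table 7 scoring rules cannot produce the SAP's own Vineland-3 standard-score range, and its AASP key does not cover the 60 items

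*SAP*

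**What the plan says.** **Vineland-3.** SAP section 4.1.3 names two kinds of derived score. It describes the first as "Standard (V-scale scores; range from 1-24" (closing bracket omitted) and the second as GSVs. It then adds: "Standard scores are scores relative to a normative age group and can range from 20-140". Protocol section 8.1.5.1 says "Standardized scores on the Adaptive Behavior Composite score range from 20 to 160".

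The derivation rules are in SAP Table 7. The ABC row maps raw scores to V-scale scores with the scoring manual. It then forms each domain standard score "as the sum of the V-scale scores within each domain", and finally: "The Vineland-3 ABC standard score will be calculated as the sum of the standard scores for the three domains". The three domain rows are worded differently. For example: "The Vineland-3 Communication standard score will be calculated as the sum of the V-scale scores within each subdomain".

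**AASP.** SAP section 4.1.3 gives 60 items and a raw-score range of 15 to 75 for every quadrant. Protocol section 8.1.5.7 gives a 5-point item scale. Table 7 lists the item numbers for each quadrant.

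**SSP-2.** SAP section 4.1.3 gives 34 items. Table 7 lists items for the sensory and behavioral scores and for four quadrants.

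**Use.** SAP section 4.2 says the primary outcome is "measured by the Vineland-3 ABC three-domain GSV composite". Appendix 1 of the SAP plans "Vineland-3 ABC Standard Score Change from Baseline", matching tables for Socialization, Communication and Daily Living Skills, an AASP quadrant table and an SSP-2 summary-score table.

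**The concern.** The SAP describes standard scores as norm-referenced on one scale and then gives a rule that yields another. No conversion follows the V-scale step, so a programmer who follows Table 7 would output sums of V-scale scores under a standard-score label. Those values could not be compared with norm-referenced Vineland-3 results. The ABC standard-score table is also the only planned output meant to be on the scale by which the protocol describes the composite.

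In the AASP, a literal reading leaves an item out of seeking. Because item 45 sits in both low registration and avoiding, at least one of those quadrants probably carries a wrong item as well. SAP Table 6 lists the AASP and SSP-2 datasets as not double programmed, so no planned second derivation would catch a key error there. The Vineland-3 dataset is double programmed, but two programmers working from the same rule would agree with each other.

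**Working it through.** **1. Vineland-3 ranges.** Inputs: V-scale 1 to 24, three subdomains per domain and nine in all (SAP section 4.1.3), and the sum rules (Table 7).

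| Score | Rule | Minimum | Maximum | Stated range |
|---|---|---|---|---|
| Domain | sum of 3 V-scale scores | 3 × 1 = 3 | 3 × 24 = 72 | 20 to 140 (SAP) |
| ABC | sum of 3 domain scores, i.e. 9 V-scale scores | 9 × 1 = 9 | 9 × 24 = 216 | 20 to 140 (SAP); 20 to 160 (protocol) |
| ABC, alternative reading | sum of 3 domain scores each already on 20 to 140 | 3 × 20 = 60 | 3 × 140 = 420 | same |

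No reading reproduces a stated range.

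- Domain: the scale 20 to 140 has 121 integer values. Those from 73 to 140, 68 in all, cannot occur under the sum rule (68/121 = 56%).
- ABC: 9 to 216 has 208 integer values. Outside 20 to 140 lie 11 (9 to 19) + 76 (141 to 216) = 87. Outside 20 to 160 lie 11 + 56 (161 to 216) = 67.

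A corrected score cannot be computed here, because the documents contain no table converting V-scale sums to standard scores.

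**2. AASP key.** The stated range comes first. With 15 items scored 1 to 5, a quadrant runs from 15 × 1 = 15 to 15 × 5 = 75, and four such quadrants use 60 items. So the description is consistent with itself. The key is not:

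| Quadrant | Entries | Range implied |
|---|---|---|
| Low registration | 15 | 15 to 75 |
| Seeking | 14 | 14 to 70 |
| Sensitivity | 15 | 15 to 75 |
| Avoiding | 15 | 15 to 75 |

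The total is 15 + 14 + 15 + 15 = 59 entries. Item 45 is in both low registration and avoiding, leaving 58 distinct items. Items 42 and 46 are in none.

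**3. SSP-2 key.** Seeking 7, avoiding 10, sensitivity 10, registration 8: 35 entries for 34 items. Item 25 is in both avoiding and sensitivity, and no item is omitted. The sensory score (items 1 to 14) and the behavioral score (items 15 to 34) do not overlap.

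**4. Control.** The same count on two other keys in Table 7 finds no fault. The RBS-R six-factor key covers 6 + 8 + 8 + 6 + 11 + 4 = 43 of 43 items once each. The CRRI key covers 12 + 11 + 20 + 11 + 8 = 62 of 62 once each.

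**5. Reach.** The Vineland-3 GSV scores are means of subdomain GSVs mapped from raw scores. They do not pass through V-scale or standard scores. The ANCOVAs, the Vineland-3 forest plots and the EEG correlations all use GSVs. The standard scores and the AASP appear only in change-from-baseline tables.

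**The case against.** The arithmetic is not in dispute. The objections concern how much to make of it.

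- **The manual is cited, so the conversion is implied.** The citation in Table 7 covers only the step from raw to V-scale scores. Where the SAP intends a final conversion it says so: the PROMIS rows map the raw sum to a T-score with the scoring manual. It does stand that the documents never describe a table from V-scale sums to standard scores, so the corrected values cannot be derived from them.
- **The AASP fault may come from PDF reading.** One number dropped from seeking and another misread as 45 would together give exactly 59 entries and 58 distinct items. This cannot be excluded, but it needs two separate faults in one key while the RBS-R and CRRI keys came through complete. Comparing the key with the original SAP and the instrument would settle it.
- **SSP-2 item 25 may be deliberate.** This stands. The documents do not say that each item belongs to one quadrant only, and the planned SSP-2 output does not name quadrants.
- **The domain-row wording has only one workable reading.** Also fair: summing within a subdomain, where there is one V-scale score, makes no sense, and the ABC row shows what is meant. It is a wording repair.
- **The two stated ranges may describe different scores.** The protocol's range is for the ABC alone, but the SAP's statement covers standard scores generally and so includes the ABC. The upper limits still conflict.
- **The integer counts do not measure impact.** Agreed. They show that the scales are incompatible and say nothing about bias.

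**Conclusion.** The concern holds. As written, Table 7 gives Vineland-3 standard scores on 3 to 72 (domain) and 9 to 216 (ABC). Neither matches 20 to 140 or 20 to 160. Its AASP key covers 58 of 60 items and puts seeking on 14 to 70 rather than 15 to 75. Four Vineland-3 tables and one AASP table are affected, and possibly the SSP-2 table if it reports quadrants and item 25 is a slip.

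All of these outputs are descriptive. The same rules apply in every arm, so the fault is one of scale and labelling and does not tilt the comparison. The primary and secondary Vineland-3 analyses are untouched. This should be corrected because named outputs would otherwise be wrong, but it does not threaten the trial's main conclusions.

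The conclusion assumes that Table 7 is programmed literally and that the AASP item numbers are as they appear in the text read from the PDF. The documents do not show where items 42 and 46 belong or which listing of item 45 is wrong.

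**What to change.** - **Vineland-3:** replace the plain sums for the domain and ABC standard scores with the norm-referenced conversion in the scoring manual that the SAP already cites, naming the tables used. This assumes the manual supplies that conversion, which the documents do not show. Use the same wording in the ABC and domain rows. In section 4.1.3, separate V-scale scores from standard scores. State one agreed range in both the SAP and the protocol.
- **AASP:** correct the key against the instrument so that each of the 60 items appears once, 15 per quadrant.
- **SSP-2:** check item 25 against the form. Remove the duplicate if it is an error, or state that the item counts in two quadrants.

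The cost is revised wording in SAP Table 7 and section 4.1.3, one range statement in the SAP or protocol, and matching programming changes. No new data are needed, and the primary and secondary analyses do not change.

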8.1.5.7 The Adolescent/Adult Sensory Profile

The Adolescent/Adult Sensory Profile (Brown and Dunn 2002) is a judgment-based self-questionnaire consisting of 60 items rated for frequency of the behavior at home or in the community. Items use a 5-point Likert scale and inquire about taste/smell processing, movement processing, visual processing, touch processing, activity level, and auditory processing. Items are factored into four sections: "Low Registration", "Sensation

Seeking", "Sensory Sensitivity", and "Sensation Avoiding". The adolescent/adult form is a unique sensory measure in that it is a self-reported questionnaire.

The questionnaire takes 10 to 15 minutes for the participant to complete.

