The PRAS-ASD is a support person-rated scale with 25 items to assess the severity of anxiety symptoms in children and adolescents with ASD. Support persons of adolescent participants will be asked to describe their child's worries and anxiety-related behaviors over the past 2 weeks on a 0 to 3-point scale from "NONE=not present", "MILD=present sometimes, not a real problem", "MODERATE=often present and a problem", and "SEVERE=very frequent and a major problem". The PRAS-ASD total score is calculated

as the sum of the scores for the 25 items. The scores range from 0 to 75, with a higher score indicating greater levels of anxiety.

Short Sensory Profile 2 (SSP-2)

The Short Sensory Profile Version 2 (SSP-2; Dunn 2014) is a 34-item parent or support person-reported questionnaire that probes for the effect of sensory processing anomalies on a person's ability to function in daily life. Item responses occur on a five-point Likert-rating scale from 1 (almost never) to 5 (almost always). The SSP-2 was based on the Sensory Processing Framework (Dunn 1999) and provides scores in four quadrants based on the child's neurological threshold to sensory input and their method of self-regulation. Raw score totals are calculated for each of the four quadrants: Seeking ("the degree to which a child obtains sensory input"), Avoiding ("the degree to which a child detects sensory input."), and Registration ("the degree to which a child misses sensory input."). A Sensory raw score and Behavioral raw score will also be calculated. The score ranges from 0 to 100 (depending on the subscale), with a higher score indicating more frequent sensory behaviors and symptoms.

Adolescent/Adult Sensory Profile (AASP)

The Adolescent/Adult Sensory Profile (Brown and Dunn 2002) is a self-reported questionnaire consisting of 60 items rated for frequency of the behavior at home or in the community. Raw score totals are calculated for each of the four quadrants: "Low Registration", "Sensation Seeking", "Sensory Sensitivity", and "Sensation Avoiding". The raw scores for each quadrant range from 15 to 75, with higher scores indicating more frequent sensory behaviors and symptoms.

Patient-Reported Outcomes Measurements Information System (PROMIS)

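### The AASP scoring key in SAP Table 7 does not match the SAP's own 60 items and 15–75 quadrant range: seeking has 14 items, items 42 and 46 are unused, and item 45 is counted twice

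*SAP*

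**What the plan says.** SAP Section 4.1.3 describes the AASP as a self-report "questionnaire consisting of 60 items rated for frequency of the behavior at home or in the community" and adds, for its four quadrants, "The raw scores for each quadrant range from 15 to 75". Protocol Section 8.1.5.7 gives the same 60 items and states "Items use a 5-point Likert scale" and "Items are factored into four sections".

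SAP Table 7 is the scoring rule. Each quadrant raw score is the sum of the items listed for it. Three of the four lists matter here:

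- The second quadrant in the table is given as "seeking (items 2, 4, 8, 10, 14, 17, 19, 28, 30, 32, 40, 47, 50 and 58".
- The first quadrant, which contains item 45, is given as "low registration (items 3, 6, 12, 15, 21, 23, 36, 37, 39, 41, 44, 45, 52, 55 and 59".
- The last quadrant, which also contains item 45, is given as "avoiding (items 1, 5, 11, 18, 24, 26, 29, 35, 38, 43, 45, 49, 53, 56 and 57".

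The remaining one, sensitivity, lists items 7, 9, 13, 16, 20, 22, 25, 27, 31, 33, 34, 48, 51, 54 and 60. SAP Appendix 1 plans a table titled "AASP Quadrant Summary Score Change from Baseline".

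**The concern.** The description of the scale and the scoring key are in the same SAP and should agree. They do not: one list is short, two items are never scored, and one item is scored twice. Table 7 is what a programmer would code from, and the quadrant scores are themselves the reported output, so an error in the key goes directly into the planned table. SAP Table 6 shows that the AASP analysis dataset is not double programmed, so that safeguard would not catch it.

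**Working it through.** **Inputs.** 60 items and a range of 15 to 75 per quadrant (SAP Section 4.1.3); a 5-point response scale and four sections (Protocol Section 8.1.5.7); four item lists, each summed (SAP Table 7).

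**Step 1: what the stated range implies.** Let a quadrant have n items scored from a to a + 4. Then n × a = 15 and n × (a + 4) = 75. Subtracting gives 4n = 60, so n = 15 and a = 1. Four quadrants of 15 make 4 × 15 = 60, the stated number of items. The SAP's description is therefore consistent with itself.

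**Step 2: count the key.**

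| Quadrant | Items listed | Range at 1–5 per item | Stated range |
|---|---|---|---|
| Low registration | 15 | 15–75 | 15–75 |
| Seeking | 14 | 14–70 | 15–75 |
| Sensitivity | 15 | 15–75 | 15–75 |
| Avoiding | 15 | 15–75 | 15–75 |

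Entries: 15 + 14 + 15 + 15 = 59. Distinct items: 58. Missing from 1–60: items 42 and 46. Duplicated: item 45, in low registration and in avoiding.

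**Step 3: possible repairs.** Assume the other 57 items are printed correctly and each item belongs to one quadrant. With item 45 taken out of both its lists, low registration, seeking and avoiding each hold 14 items and sensitivity holds 15 (14 + 14 + 14 + 15 = 57). Items 42, 45 and 46 fill the three gaps in 3! = 6 ways.

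| Where item 45 belongs | Repairs | Seeking as printed | Low registration as printed | Avoiding as printed |
|---|---|---|---|---|
| Low registration | 2 | wrong | right | wrong |
| Avoiding | 2 | wrong | wrong | right |
| Seeking | 2 | wrong | wrong | wrong |

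Seeking is wrong in 6 of 6, and at least one of low registration and avoiding is wrong in 6 of 6. Both are wrong in 2 of 6. Sensitivity shows no fault.

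**Step 4: size for one participant.**

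- One item omitted (seeking): the raw score is 1 to 5 points too low. The change score is off by at most 5 − 1 = 4.
- One wrong item in place of the right one: the raw score is off by at most 5 − 1 = 4. The change score is off by at most 4 − (−4) = 8.
- If all 15 seeking items changed by the same amount (an assumption), the mean seeking change would be understated by 1/15 = 6.7%.

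**Step 5: reach.** Protocol Table 9 makes the AASP mandatory for high-functioning participants and not applicable to low-functioning ones. Low-functioning participants are capped at 25%.

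- Cap filled, non-evaluability unrelated to IQ: 0.75 × 84 = 63 of the planned 84 evaluable.
- Cap filled and every low-functioning participant evaluable: 0.25 × 105 = 26.25, so at most 26, leaving 84 − 26 = 58.
- Cap not filled: more than 63 under proportional evaluability, up to 84.

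The number falls if some high-functioning participants cannot self-report and switch to the SSP-2 (Protocol Table 9, footnote 1).

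**Comparison with other keys in Table 7.** The CRRI lists cover items 1–62 exactly once (12 + 11 + 20 + 11 + 8 = 62). The six-factor RBS-R lists cover 1–43 exactly once (6 + 8 + 8 + 6 + 11 + 4 = 43).

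**The case against.** The strongest reply is that only the 14-item seeking list directly contradicts the stated range. No sentence says that every AASP item is scored exactly once. One could add an item to seeking, leave 45 in both lists and leave one item unscored, and all four ranges would then be 15–75. That reading is possible but strained: 60 items factored into four sections, with four ranges that each need 15 items, point strongly to a clean division. It does mean that the count of at least two wrong quadrants carries a condition.

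A second point is that the lists are printed in ascending order. Item 46 would fit the place of either 45 (between 44 and 52, or between 43 and 49), while 42 fits neither place. A simple misprint therefore suggests that 46 became 45 in one list and 42 dropped out of seeking, which is 2 repairs rather than 6. This is useful evidence about the likely slip, but it does not say which list is wrong. It leaves seeking and one other quadrant at fault.

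Third, the fault might come from reading the PDF. That cannot be excluded without the source page, but one misread number would not explain both the short list and the duplicate.

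Fourth, the effect is small, and this stands. The AASP is exploratory (Protocol Table 6), summarised descriptively (SAP Section 4.3), and absent from the main ANCOVA analyses and the listed subgroup analyses. The 4- and 8-point figures are individual worst cases, and no bias between arms has been shown. Table 7 also cites the instrument, so a programmer working from the form might never use the faulty lists.

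**Conclusion.** The point holds. The printed key cannot produce the stated 15–75 range for seeking, and it uses 58 of the 60 items. The seeking contradiction needs no assumption beyond the documents' own figures. The conclusion that at least two of four quadrants are mis-scored assumes that each item belongs to one quadrant, and that the key is programmed as printed. The count of six repairs further assumes that the other 57 items are correct. The documents do not establish where items 42, 45 and 46 belong.

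The damage is confined to an exploratory descriptive table, so the error is minor in consequence. It is still a definite error in an operative scoring rule and worth correcting.

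**What to change.** 1. Look at the source page of SAP Table 7 to rule out a PDF-reading fault.
2. If the fault is real, correct the lists against the cited AASP scoring form so that the four quadrants divide items 1–60 into four sets of 15. A program check that each item appears exactly once would confirm this.
3. Confirm that the AASP dataset is programmed from the corrected key.
4. At the same sitting, look up SSP-2 item 25, which Table 7 lists under both avoiding and sensitivity. This is a query only: no item count or range is stated for each SSP-2 quadrant, and no SSP-2 item is missing.

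The cost is one look-up and a correction to at least two lists if the items divide cleanly. Because the SAP is signed, the correction needs a new version or a documented note. There is no statistical downside.

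### SAP Table 7 scores SSP-2 item 25 in both the avoiding and the sensitivity quadrant, so at least one of those two scores is wrong as written

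*SAP*

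**What the plan says.** SAP Section 4.1.3 says the SSP-2 "is a 34-item parent or support person-reported questionnaire", with responses on a "five-point Likert-rating scale from 1 (almost never) to 5 (almost always"), and that it "provides scores in four quadrants based on the child's neurological threshold to sensory input" and self-regulation. Protocol Section 8.1.5.8 gives the same scale length and item range.

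SAP Table 7 then splits the items in two ways. The first split has two parts: "The SSP-2 sensory raw score will be calculated as the sum of the scores for items 1-14", and "The SSP-2 behavioral raw score will be calculated as the sum of the scores for items 15-34". The second has four quadrants:

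- "seeking (items 6-8, 11, 14, 31 and 32")
- "avoiding (items 16-20 and 22-26")
- "sensitivity (items 1-5, 21, 25, 28, 29 and 33")
- registration, with items 9, 10, 12, 13, 15, 27, 30 and 34.

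The SAP does not say that an item may count in two quadrants. For the key it refers to the SSP-2 caregiver questionnaire. SAP Section 4.3 plans descriptive summaries of the SSP-2 by arm at baseline, at Week 12 and for the change between them. SAP Table 6 marks the dataset ADSSP as not double-programmed.

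**The concern.** Item 25 lies inside the run 22-26 under avoiding and is named again under sensitivity. A programmer who follows the table literally will add it to both raw scores. One quadrant is then inflated by an item that belongs elsewhere, and a real change on that item appears as movement in two sensory constructs.

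The people affected are those for whom the SSP-2 is completed. Protocol Table 9 makes it mandatory for all adolescents and for low-functioning adults. It is the only sensory measure listed for low-functioning participants, because the self-reported sensory profile (AASP) is not applicable to them. Under the table's first footnote it also replaces the AASP when a participant cannot self-report.

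**Working it through.** **Inputs.** Scale length of 34 and item range of 1 to 5: SAP Section 4.1.3. Item lists: SAP Table 7.

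**Step 1: the two-way split reproduces the scale length.** Items 1-14 are 14 items and items 15-34 are 20. 14 + 20 = 34, each item used once. Possible range of the sum: 34 × 1 to 34 × 5, or 34 to 170.

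**Step 2: expand the quadrant key.**

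| Quadrant | Items | Entries | Range at 1-5 |
|---|---|---|---|
| Seeking | 6, 7, 8, 11, 14, 31, 32 | 7 | 7-35 |
| Avoiding | 16, 17, 18, 19, 20, 22, 23, 24, **25**, 26 | 10 | 10-50 |
| Sensitivity | 1, 2, 3, 4, 5, 21, **25**, 28, 29, 33 | 10 | 10-50 |
| Registration | 9, 10, 12, 13, 15, 27, 30, 34 | 8 | 8-40 |
| Total | 34 distinct items | 35 | 35-175 |

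7 + 10 + 10 + 8 = 35. All items from 1 to 34 appear, none is out of range, and item 25 is the only repeat.

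**Step 3: size of the error.** Let *x* be a participant's score on item 25. On a complete form:

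seeking + avoiding + sensitivity + registration = sensory + behavioral + *x*, with *x* between 1 and 5.

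The faulty quadrant is therefore too high by 1 to 5 points at each visit. For change from baseline, the error is the change in *x*, which lies between 1 − 5 = −4 and 5 − 1 = +4. For a comparison of arms, the error in the difference of mean changes is the between-arm difference in mean change on item 25. It is zero if item 25 moves equally in both arms.

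**Step 4: remove the duplicate.** Either removal gives 34 entries with each item used once.

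| Item 25 removed from | Avoiding | Sensitivity | Total entries |
|---|---|---|---|
| Avoiding | 9 items, 9-45 | 10 items, 10-50 | 34 |
| Sensitivity | 10 items, 10-50 | 9 items, 9-45 | 34 |

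The documents do not show which is right.

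**Step 5: is the overlap deliberate?** Compare the other keys in Table 7. The six RBS-R subscales have 6 + 8 + 8 + 6 + 11 + 4 = 43 items, a clean partition of 43. The five CRRI subscales have 12 + 11 + 20 + 11 + 8 = 62, a clean partition of 62. The AASP key next to the SSP-2 has 15 + 14 + 15 + 15 = 59 entries for 60 items: item 45 appears under both low registration and avoiding, items 42 and 46 are absent, and seeking has 14 items. SAP Section 4.1.3 gives every AASP quadrant a range of 15 to 75, which needs 15 items scored 1 to 5. Both sensory keys therefore look mistranscribed, while the other two subscale keys do not.

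**The case against.** The count is not in dispute. The strongest objection is that neither document says an item belongs to exactly one quadrant, or that the quadrants must add up to sensory plus behavioral. Only the cited questionnaire can settle that. This is fair as far as it goes: one quadrant per item is an inference. It is a strong one, because 33 of the 34 items are used once, none is omitted, and no shared item is flagged.

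Several points on importance stand:

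- The SSP-2 is exploratory and descriptive. It has no planned ANCOVA, p-value, forest plot or biomarker correlation. The surplus in the level cancels in change from baseline unless item 25 itself changes, and 4 points is an individual extreme, not a plausible group difference.
- The planned output is titled only as an SSP-2 summary score, whereas the AASP table names quadrants. The SAP says quadrant scores will be calculated, but the output list does not confirm that they will be tabulated.
- High-functioning adolescents also complete the AASP, so the SSP-2 is not their only sensory measure. Low-functioning participants are capped at 25%. For low-functioning adults the SSP-2 is optional in protocol Table 6 but mandatory in Table 9, so fewer may contribute.
- SAP Section 4.1.3 also gives SSP-2 scores a range starting at 0, which items scored 1 to 5 cannot produce. The ranges above rest on the 1-to-5 scoring.

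These points limit the consequence. None of them removes the duplicate.

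**Conclusion.** The concern holds. The quadrant key in SAP Table 7 has 35 entries for 34 items, and item 25 is scored in two quadrants. Programmed as written, at least one of avoiding and sensitivity is wrong for every SSP-2 respondent: 1 to 5 points too high at each visit, and off in change from baseline by the change on item 25, within 4 points either way. This assumes that items are scored 1 to 5, that each item belongs to one quadrant, and that the form is complete. The sensory and behavioral raw scores, the other two quadrants and all primary and secondary endpoints are unaffected. It is a small error in an exploratory measure, but it is an operative scoring rule and no independent program is planned that would expose it. It should be corrected.

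**What to change.** Look up item 25 in the SSP-2 caregiver questionnaire that the SAP cites and list it in one quadrant only. If it belongs to sensitivity, break the run 22-26 under avoiding. If it belongs to avoiding, delete it from the sensitivity list. Add a check to the ADSSP derivation that, on each complete form, the four quadrant scores sum to sensory plus behavioral. Any SSP-2 quadrant scores already derived from the current key should be re-derived.

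The cost is one line in SAP Table 7 and one programming check. In the same pass, check the AASP key against its own questionnaire (item 45 listed twice, items 42 and 46 absent), and reconcile the SSP-2 score range in SAP Section 4.1.3 with items scored 1 to 5.
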